9.2 Prohibited Medications

Any subject with insulin-dependent diabetes taking insulin will be excluded from the study. Subjects taking medications that may negatively affect their cognition may be excluded from the study at time of screening. Exceptions will be made if such treatment is discontinued within 30 days or if the subject only takes low or infrequent doses of the medication that are unlikely to affect cognition, at the investigators discretion. These medications include anticholinergics, and centrally acting antihistamines (e.g. Benadryl), opiates, benzodiazepines, barbiturates, muscle relaxants.

10 Subject Completion and Withdrawal

10.1 Subject Completion

Subjects completing all 3 study visits will be considered to have completed study.

10.2 Subject Withdrawal

Subject may withdraw from study at any time for any reason without penalty or be terminated from the study by the clinical investigator (see provisions for termination by study team.) Investigational team will document the reason(s) for withdrawal. In the event a subject chooses to withdraw from study before Visit 3, the safety procedures described in Section 7.3 will be performed ideally within 3 days following subject's decision to withdraw. For all subjects who withdraw, all final safety assessments will be collected regardless of time elapsed since previous visit. In addition to the termination visit, subjects who withdraw early will be contacted within 7 days by study staff via telephone to assess development

of new and/or ongoing AEs and concomitant medications. Efforts will be made to recruit subjects to replace any withdrawals before randomization so as to maintain an n=30.

Subject's participation may be terminated at the discretion of the investigator. Individuals may be withdrawn for the following reasons:

- Clinically significant adverse events
- Lost to follow-up
- Protocol violations
- Inability to tolerate study medication
- Other

11 Adverse Events (AE) and Serious Adverse Events (SAE)

11.1 Definition of AE

An adverse event is any symptom, sign, illness or experience which develops or worsens in severity during the course of the study. Intercurrent illnesses or injuries should be regarded as adverse events. Abnormal results of diagnostic procedures are considered to be adverse events if the abnormality:

- Results in study withdrawal
- Is associated with clinical signs or symptoms
- Leads to treatment or to further diagnostic tests
- Is considered by the investigator to be of clinical significance

11.2 Definition of SAE

Adverse events are classified as either serious or non-serious. A serious adverse event is any event that results in:

- Death
- Life-threatening situation
- Hospitalization or prolongation of hospitalization
- Disability or incapacitation
- Other events determined by investigator to be medically significant in which subject's well-being is jeopardized (e.g. events that have high likelihood of escalating to the point of meeting criteria outlined above)

11.2.1 Clinical Laboratory Abnormalities & Other Abnormal Assessments as AEs & SAEs

Any new abnormal, vital, examination, or laboratory finding judged clinically significant by the investigator will be documented as an AE or SAE, if meeting the definitions for such. Abnormal lab findings or other abnormal assessments associated with the disease under study will not be considered AEs or SAEs unless more severe than expected, as judged by the investigator.

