1.1.2 PD and Insulin

Historically insulin was thought solely to be a peripherally acting hormone responsible for glucose homeostasis and energy metabolism. However, accumulating evidence indicates insulin can cross the blood-brain-barrier and influence a multitude of processes in the brain including regulating neuronal survival and growth, dopaminergic transmission, maintenance of synapses and pathways involved in cognition (Athauda and Foltynie, 2016).

Multiple research studies have identified links between PD and type 2 diabetes mellitus (T2DM), particularly highlighting associations between Parkinson's disease pathogenesis and the mechanisms underlying the development of insulin resistance. A recent large cohort study by De Pablo-Fernandez et al. (De Pablo-Fernandez et al., 2018), reported an increased rate of subsequent PD in T2DM, suggesting a shared genetic predisposition and/or disrupted shared pathogenic pathways.

Both insulin and glucagon-like peptide 1 agonists (GLP-1) have previously been found to have neuroprotective effects in animal models of synucleinopathies, including PD and multiple system atrophy (Bassil et al., 2017), possibly due to effects on neuronal survival and growth, maintenance of

synapses, and dopaminergic transmission. Insulin deficiency or resistance has been implicated in the pathogenesis of several neurodegenerative diseases (Jankovic, 2017).

A review article by Aviles-Olmos et al. (2013) highlights varying associations between diabetes or abnormal glucose tolerance and sporadic forms of Parkinson's disease from both cross-sectional and cohort studies. Survey data reveal that diabetes is established in 8–30% of patients with PD, consistently in excess of the prevalence found in non-Parkinson's disease individuals (Chalmanov and Vurbanova, 1987; Pressley et al., 2003). Another investigation found no link between the two diseases: A meta-analysis of 14 studies comprising a total of 21,395 patients with PD and 84,579 individuals without PD found a negative association between T2DM and PD (Lu et al., 2014).

A case control study showed that patients with PD dementia had a higher prevalence of abnormal glucose metabolism, mainly insulin resistance, than non-demented patients with PD (Bosco et al., 2012). Another study found that patients with PD and comorbid DM exhibited increased impairment in attentional function and executive function deficits than PD patients without DM (Ashraghi et al., 2016).

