4.1 Primary Endpoints

- Composite safety event of either: a reduction of fasting glucose to <70 mg/dL or an unintended reduction of weight >5%
- Pre-post change in safety measures (fasting glucose and weight)
- Number of AEs and SAEs

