4.3 Safety

- Incidence and severity of serious adverse events (SAEs) and adverse events (AEs)
- Frequency of change in clinically-significant vital signs, physical exam or neurological exam
- Plasma glucose level <70mg/dl
- Change in weight

5 Study Design

This study is a single center trial to determine dose finding, safety and tolerability of 3 doses of intranasal (IN) regular insulin (Table #2) and placebo in patients with Parkinson's disease.

Table 2: Intranasal Drug Dosing

Group	Drug	Dose	Volume	N=
Dose group 1	Insulin	20 IU/IN (10 IU, one nostril, twice daily)	100µl	7
Dose Group 2	Insulin	40 IU/IN (10 IU, each nostril, twice daily)	100µl	7
Dose Group 3	Insulin	80 IU/IN (20 IU, each nostril, twice daily)	200µl	9
Dose Group 4	Placebo	0.9% Saline (each nostril, twice daily)	200µl	7

After written informed consent has been obtained from the subject and family member/caregiver, subjects will be screened to assess study eligibility based on study inclusion/exclusion criteria. Subjects who are eligible at the end of the screening visit (Visit 1) will be scheduled for a baseline and randomization visit (Visit 2). During the baseline visit, subjects will be administered a cognitive battery. Subjects will also undergo a neurological examination, including the UPDRS (United Parkinson's Disease Rating Scale- MDS) to be performed in the "ON-STATE" (after taking Anti-Parkinson's medications according to the subject's regular medication schedule). A final safety/assessment visit will take place 3 weeks after visit 2 at which time the tests will be re-administered.

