7.3 Safety

For all safety assessments described below, any clinically significant change will be recorded as an AE or SAE.

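### A clinically significant worsening of a Parkinson's-type finding is an AE under Sections 7.3 and 11.1 but may not be under 11.2.1, and the AE count is a primary endpoint

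*Combined protocol and SAP*

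**What the plan says.** Three sections decide whether an abnormal finding is recorded.

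- Section 7.3, whose subsections cover physical and neurological examination, vital signs, weight, ECG and laboratory samples: "For all safety assessments described below, any clinically significant change will be recorded as an AE or SAE".
- Section 11.1: "An adverse event is any symptom, sign, illness or experience which develops or worsens in severity during the course of the study". It also makes an abnormal diagnostic result an AE if it causes withdrawal, comes with signs or symptoms, prompts treatment or more tests, or is clinically significant in the investigator's view.
- Section 11.2.1 has two sentences. The first documents new vital-sign, examination or laboratory findings that the investigator judges clinically significant. The second reads: "Abnormal lab findings or other abnormal assessments associated with the disease under study will not be considered AEs or SAEs unless more severe than expected", again on the investigator's judgement.

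Sections 7.3.1 and 7.3.2 assign abnormalities seen at Visit 1 to medical history. Section 4.1 lists "Number of AEs and SAEs" as a primary endpoint, and Section 4.3 lists "Frequency of change in clinically-significant vital signs, physical exam or neurological exam" as a safety item. Section 12.2 summarises AEs and SAEs by group and adds a chi-square test only where a spike is noticed.

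**The concern.** Sections 7.3 and 11.1 have no disease exception and Section 11.2.1 has one. Nothing says which governs, and nothing says what severity is expected over a three-week treatment period or against which visit it is judged. Two investigators who see the same worsened examination could both follow the protocol and record different counts.

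Section 1.1.4 says that the authors know of no published trial of intranasal insulin in PD. Whether the drug worsens PD-type findings is therefore part of the safety question, and the exemption applies to just those findings. The randomised placebo arm already supplies their background rate, so a filter based on expectation is not needed for that purpose. A lower count also makes it less likely that anyone notices the spike that triggers a test under Section 12.2. The exemption names SAEs as well as AEs, and Section 13.2 makes the SAE rate a ground for stopping the study, with details left to the DSMB charter.

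**Working it through.** **The three rules applied to the same findings**

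| Finding at Visit 3 | 7.3 | 11.1 | 11.2.1 |
|---|---|---|---|
| PD sign present at Visit 1, unchanged | Not an AE | Not an AE | Not an AE |
| PD sign present at Visit 1, worse to a clinically significant degree, judged in line with PD | AE | AE | First sentence silent (not new); second sentence: not an AE |
| New, clinically significant, PD-associated, judged in line with PD (such as an orthostatic drop) | AE | AE | First sentence: AE; second sentence: not an AE |
| PD-associated worsening, clinically significant, judged worse than expected | AE | AE | AE |

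The sections agree in the first and last rows and conflict in the middle two. A further conflict lies between 11.1 and 11.2.1 alone: a disease-associated abnormal result that leads to withdrawal is an AE under 11.1, and not under 11.2.1 if it is judged expected.

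**What can be computed**

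The only related figure in the plan is the sample size. Table 2 gives 7 + 7 + 9 + 7 = 30, which matches the stated accrual. The plan sets no power, alpha or AE rate, so the following only illustrates the mechanism.

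Let p be the true share of participants in an arm with a PD-type worsening, and q the share of those left unrecorded under 11.2.1. Both are assumed, with at most one such event per participant. The chance that an arm of size n shows at least one recorded event is 1 − (1 − p(1 − q))^n. With p = 0.20:

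| q | n = 7 | n = 9 |
|---|---|---|
| 0 | 1 − 0.80^7 = 0.79 | 1 − 0.80^9 = 0.87 |
| 0.25 | 1 − 0.85^7 = 0.68 | 1 − 0.85^9 = 0.77 |
| 0.50 | 1 − 0.90^7 = 0.52 | 1 − 0.90^9 = 0.61 |
| 0.75 | 1 − 0.95^7 = 0.30 | 1 − 0.95^9 = 0.37 |

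Going from q = 0 to q = 0.50, the chance falls from 0.52 to 0.30 (n = 7) and from 0.61 to 0.37 (n = 9) at p = 0.10. At p = 0.30 it falls from 0.92 to 0.68 and from 0.96 to 0.77.

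**Effect on the comparison with placebo**

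If q is the same in every arm, the recorded difference is (1 − q)(p_insulin − p_placebo). With 0.30 against 0.10 and q = 0.50, a true difference of 0.20 is recorded as 0.50 × 0.20 = 0.10. This needs q to be similar across arms. If every insulin event were kept (q = 0) and half the placebo events were not, the recorded difference would be 0.30 − 0.05 = 0.25, larger than the truth.

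**The case against.** **It means only known PD signs.** On this reading new findings are recorded, and established PD abnormalities are not recorded again unless they are worse than expected. That is a natural intention, but the text does not state it. Sections 7.3.1 and 7.3.2 already send Visit 1 examination abnormalities to medical history, so for those the sentence would largely repeat them. The first sentence of 11.2.1 protects new findings only, not the worsening of an existing sign.

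**The exemption is narrow.** It covers abnormal labs and assessments, and 11.1 still counts symptoms, signs and illnesses. This stands in part. However, a worsened neurological examination is both a sign and an abnormal assessment, so it falls under both rules.

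**Other outcomes show the harm.** UPDRS III, cognition, mood and apathy are measured at Visits 2 and 3 and reported by arm as mean changes with 95% confidence intervals (Section 12.3). This also stands in part. A group mean can hide one participant's worsening, Table 3 marks none of these tests at early withdrawal, and Section 12.2 gives no analysis of the 4.3 examination and vital-sign item.

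**Removing equal background events from each arm leaves the absolute difference unchanged.** This is correct arithmetic. It requires the investigator to leave out background events but keep drug-caused ones. Under blinding, the only thing that could separate them is severity. Shrinkage is therefore conditional on a similar share being left out in every arm, and it is not a general result.

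**The analysis is descriptive and unpowered** (Section 12.4). That is true, and it limits the consequence. It does not tell the investigator which rule to follow.

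**Conclusion.** The contradiction is on the page. A clinically significant on-study worsening of a PD-type finding is an AE under 7.3 and 11.1 and may not be one under 11.2.1. This can lower the primary count of AEs and SAEs. It shrinks an insulin-placebo difference if blinded investigators leave out a similar share of such events in every arm. The size cannot be calculated from the documents, because neither the rate of such findings nor the share left out is given.

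A reader might infer more than this, and the documents do not support it:

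- *That PD-like harms vanish from the trial.* Findings judged worse than expected are kept, and motor, mood and cognitive changes are reported separately.
- *That low glucose could be filtered out*, since Section 1.1.2 reports that "diabetes is established in 8–30% of patients with PD". The disease under study is PD, and the same section also cites a meta-analysis with a negative association. Section 7.3.3 declares glucose below 70 mg/dL clinically significant. The composite, glucose and weight endpoints are measured directly and do not depend on 11.2.1.
- *That mood and cognitive tests are part of the conflict with 7.3.* They are described in Section 7.5, outside the list that the 7.3 rule covers.
- *That each omitted participant moves an arm by 1/7 = 14.3 or 1/9 = 11.1 percentage points.* The endpoint is a number of events, not a proportion of participants. Even a proportion would move only if that participant had no other AE, and Section 1.1.5 names transient nasal irritation as the most common side effect.

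**What to change.** Reconcile Sections 7.3, 11.1 and 11.2.1 before unblinding by replacing the second sentence of 11.2.1 with:

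- Findings present before the first dose and unchanged are medical history.
- Any clinically significant worsening from the last pre-dose assessment of that measure (Visit 2 where done, otherwise Visit 1) is recorded as an AE or SAE, whether or not it is attributed to PD.

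Under 7.3.2 the reference for the neurological examination is then Visit 1. For orthostatic vital signs it is the Visit 2 average that 7.3.3 already specifies. Record the investigator's view on PD as the cause in a separate CRF field, and do not use that field to exclude events from the counts in 12.2.

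Clinical significance remains a judgement, but 7.3 and 11.1 already use that threshold, so no new one is added. The undefined expectation is replaced by a measured reference.

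The cost is one sentence, one CRF field and slightly more AEs to record. Raw totals will be higher in every arm, placebo included. Treatment and visits do not change.

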11.2.2 Time Period and Frequency of Detecting AEs and SAEs

Upon consenting, a subject is considered to be a participant in the study, and until that person either withdraws or completes study, AEs and SAEs will be recorded. The investigational team will promptly report any AE/SAE as required per federal guidelines.

11.2.3 SipNose Failures and Malfunctions

Device Quality Control. All failures and Malfunctions of the device must be documented on the Device Malfunction/Performance Form. All performance issues and malfunctions will be reported to SipNose and in the clinical results (e.g., final report).

12 Data Analysis and Statistical Considerations

12.1 Statistical Analysis Overview

Due to the small sample size of this study, statistical analysis will be mainly exploratory and descriptive: t-tests (or Mann-Whitney u-tests if normality of the data is not met) are used to compare the difference of a continuous measure between groups (such as patient age at baseline, various efficacy measures), and contingency tables and chi-square tests are used to compare the difference of a categorical variable (such as patient gender at baseline, various safety and adverse events).

To minimize the potential confounding effects of gender and MOCA score on the treatment effect, we will use stratified block randomization when assigning patient to one of the four study groups. The stratification factors will be gender (male/female) and MOCA score (low <22/30 and high>23/30). We will use block size of four.

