
Primary Objectives:
 
 • To determine the safety and tolerability of three different doses of intranasal insulin in patients with Parkinson's disease (PD) 	

Secondary Objectives:
 
 • To evaluate efficacy of intranasal insulin on cognitive functioning in PD • To evaluate efficacy of intranasal insulin on motor function in PD • To evaluate efficacy of intranasal insulin on mood and apathy in PD • To identify which outcome measures are most sensitive to effects of intranasal insulin in PD 	
STUDY DESIGN	
Study Type	Dose-finding
Control Type	None
Study Indication Type	Dose-finding, safety
Blinding Schema	Double blinded
Device	SipNose nasal device
Study Design	randomized, parallel-group, double blind, placebo-controlled
Planned Duration of Subject Participation	8 weeks (Treatment duration: 3 weeks)
PRIMARY ENDPOINTS	

 • Composite safety event of either: a reduction of fasting glucose to <70 mg/dL or an unintended reduction of weight >5% • Pre-post change in safety measures (fasting glucose and weight) • Number of AEs and SAEs 	
SECONDARY ENDPOINTS	

 • Pre-post change in cognitive function measures 	

 • Pre-post change in motor function measures • Pre-post change in mood and apathy measures 	
INVESTIGATIONAL PRODUCTS, DOSE AND MODE OF ADMINISTRATION	
Investigational Product	
Regular insulin (Novolin-R) in 3 different doses and placebo
 
Dose 1, group with 7 participants: 20 IU/IN (10 units IN in one nostril twice daily x 21 days, volume 100 µl)
 
Dose 2, group with 7 participants : 40 IU/IN (10 units IN in each nostril twice daily x 21 days, volume 100 µl)
 
Dose 3, group with 9 participants: 80 IU/IN (20 units IN in each nostril twice daily x 21 days, volume 200 µl)
 
Dose 4, group with 7 participants: placebo (each nostril, twice daily)

SUBJECT SELECTION	
Targeted Accrual	30 subjects. We estimate a need to consent 50 participants in order to reach this goal.
INCLUSION CRITERIA	

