12.2 Statistical Analysis of Primary Aim – safety, tolerability and adverse events

To assess safety and tolerability of the study drug at varying dose levels, AEs and SAEs will be categorized and summarized by study group. We will descriptively note if any group was more likely to have experienced a particular AE/SAE or generally experienced more AEs/SAEs throughout the course of the study; if we notice a significant ‘spike’ associated with a particular dosing group for a certain event, we’ll construct a chi-square test to see if it’s statistically significant. We will also assess the number of and reason for early withdrawals in each study group.

We will also monitor two key safety measures: 1) a fasting glucose < 70 mg/dL and 2) an unintended weight loss of >5% (relative to the patient’s weight at visit 2). The number of participants in each group who experience either or both of these events will be counted and descriptively compared. We will then compare the change in fasting glucose and weight at Visit 2 (Baseline/Initial Treatment) and Visit 3 (Final Treatment/Safety). In the event of an early withdrawal, measures taken at the early withdrawal visit will be used in place of Visit 3 data. We will descriptively note if any dosing group was more inclined to experience one or both of these safety events. In a similar fashion, if we notice a significant ‘spike’ associated with a particular dosing group, we’ll construct a chi-square test to see if it is statistically significant.

Secondarily, we will report the incidence of mild, moderate, and severe hypoglycemia overall and by group. Mild hypoglycemia will be defined as $54 \text{ mg/dL} \leq \text{fasting glucose} < 70 \text{ mg/dL}$; moderate hypoglycemia is $40 \text{ mg/dL} \leq \text{fasting glucose} < 54 \text{ mg/dL}$; and severe hypoglycemia is $\text{fasting glucose} < 40 \text{ mg/dL}$.

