12.4 Statistical Power

As stated above, due to the sample size limitation of this study, no particular statistical power is under consideration during the study design phase with the intent to detect a meaningful clinically significant difference between study groups for any of the primary or secondary outcome measures; statistical analysis of this study will be mainly exploratory and descriptive.

The overall goal of the study is to identify a safe dose intranasal insulin with trends towards the secondary outcomes. Three different doses (and placebo) will be used, with the highest number of subjects (9) in the group with the highest dose, a model previously used by Finger et al. (2014).

13 Study Conduct Considerations

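### Chi-square is the only test named for categorical and safety data, but arms of 7, 7, 9 and 7 cannot give adequate expected counts; exact tests should replace it

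*Combined protocol and SAP*

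**What the plan says.** Section 12.1 gives the general rule that "contingency tables and chi-square tests are used to compare the difference of a categorical variable", with baseline gender and safety and adverse events as its examples. The same sentence gives continuous data a fallback (Mann-Whitney when normality fails) but gives categorical data none.

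Section 12.2 summarises adverse events, and the glucose and weight events that form the primary composite, by group and compares them descriptively. If a spike is noticed in a particular dosing group, the statistician will "construct a chi-square test to see if it is statistically significant". The section names chi-square in this role twice: once for adverse events and once for the glucose and weight events.

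Neither section says whether that test covers all four arms, one arm against placebo or one arm against the rest, or whether a continuity correction is used. Section 12.4 plans no power and explains the unequal allocation, "with the highest number of subjects (9) in the group with the highest dose".

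**The concern.** The chi-square p-value relies on a large-sample approximation that is usually trusted only when expected counts are about 5 or more. The arm sizes are fixed in advance, so it can be seen now whether any outcome of this trial could meet that condition.

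At stake is whether an excess of a primary safety event in one dose group is labelled statistically significant. Section 12.4 gives the overall aim as finding a safe dose, and such a label would colour that judgement even though no formal rule depends on it. A noticed spike is by nature a sparse table with its events concentrated in one arm, and in such two-group tables the approximate and exact p-values can differ widely.

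**Working it through.** **Inputs.** Arm sizes come from the Protocol Summary and agree with Table 2 in Section 5: "Dose 1, group with 7 participants", "Dose 2, group with 7 participants", "Dose 3, group with 9 participants" and "Dose 4, group with 7 participants" (placebo). 7 + 7 + 9 + 7 = 30, which matches the targeted accrual. The plan gives no test level and no safety event rate. I assume a two-sided 0.05 level and a common event rate between 2% and 50% under the null. The plan states no figure of its own to reproduce.

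**Expected counts.** With m events among N participants, the smallest expected cell is n × min(m, N − m)/N, where n is the smallest arm in the table. Every cell reaches 5 only if both n·m/N ≥ 5 and n·(N − m)/N ≥ 5.

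| Table | Events needed for both conditions | Largest possible value of the smallest cell |
|---|---|---|
| 7/7/9/7 | m ≥ 22 and m ≤ 8 | 7 × 15/30 = 3.5 |
| 7 v 7 | m ≥ 10 and m ≤ 4 | 7 × 7/14 = 3.5 |
| 9 v 7 | m ≥ 12 and m ≤ 4 | 7 × 8/16 = 3.5 |
| 7 v other 23 | m ≥ 22 and m ≤ 8 | 7 × 15/30 = 3.5 |
| 9 v other 21 | m ≥ 17 and m ≤ 13 | 9 × 15/30 = 4.5 |

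No row can be satisfied. Cochran's rule (at most 20% of cells below 5, none below 1) also fails for every m. At least 4 of the 8 cells are below 5 in the four-arm table, and at least 1 of 4 (25%) in each two-group table. Dropout would only lower these counts.

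**Effect on two-group p-values.** Uncorrected Pearson is N(ad − bc)²/(product of the four margins).

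- 4/7 v 0/7: 14 × 28²/(7 × 7 × 4 × 10) = 5.60, p = 0.018. Fisher: 2 × 35/1001 = 0.070.
- 2/9 v 0/21: 30 × 42²/(9 × 21 × 2 × 28) = 5.00, p = 0.025. Fisher: 36/435 = 0.083.

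Yates' correction subtracts N/2 from |ad − bc|. The first statistic becomes 14 × 21²/1960 = 3.15 (p = 0.076) and the second 30 × 27²/10584 = 2.07 (p = 0.151). The plan's wording therefore permits either side of 0.05 from the same data.

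**True size at nominal 0.05, by full enumeration.**

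| Event rate | Four-arm chi-square | 9 v 7, uncorrected chi-square | 9 v 7, Fisher |
|---|---|---|---|
| 5% | 0.004 | 0.003 | 0.0001 |
| 10% | 0.015 | 0.015 | 0.002 |
| 20% | 0.037 | 0.051 | 0.010 |
| 30% | 0.049 | 0.073 | 0.020 |
| 50% | 0.052 | 0.081 | 0.025 |

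Maximum size over 2% to 50% for the other uncorrected two-group tests is 0.057 (7 v 7), 0.058 (7 v 23) and 0.055 (9 v 21). Fisher-Freeman-Halton on four arms peaks at 0.046. Of the 5,120 possible four-arm tables, chi-square and the exact test disagree at 0.05 in 148: 110 are significant by chi-square only and 38 by the exact test only.

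**The case against.** The strongest reply is that little rests on these p-values. Section 12.1 declares the analysis mainly exploratory, Section 12.4 disclaims power, and Section 12.2 compares safety events descriptively before any test. The protocol ties no dose choice or stopping decision to a p-value; Section 13.2 leaves stopping details to the DSMB charter. All of this stands, and it limits the severity.

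The second reply is that the four-arm chi-square behaves acceptably. Its size does not exceed 0.052, and under a looser rule (all expected counts at least 1) tables with 5 to 25 events pass. That also stands. However, the plan does not say that the follow-up test is four-arm. A spike in one dosing group could equally be tested against placebo or against the rest.

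The third reply is that the two-group examples use uncorrected Pearson and have no events in the comparator. With Yates' correction both p-values exceed Fisher's (0.076 v 0.070 and 0.151 v 0.083). This is correct. It means that the direction of error depends on a choice that the plan leaves open.

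A reader might infer that chi-square is prescribed for every safety comparison, or that the primary safety p-values are simply wrong and always too small. The documents support neither reading. Testing is conditional on a noticed spike, and the approximation errs in both directions.

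**Conclusion.** The point holds as one of test choice, at minor to moderate severity. For every per-arm comparison that the plan implies, the expected counts fall short of the usual rule whatever the data show, and no exact test is named. The distortion is greatest in two-group contrasts, where uncorrected size reaches 8.1% for 9 v 7. For rare events the four-arm test rejects far less often than 5%.

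These sizes assume a two-sided 0.05 level, full arms and independent participants with a common event rate. The only exception found to the expected-count result is a pooled 14 v 16 table, which meets the rule with 11 to 19 events, but no such pooling is planned.

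One might also infer that exact tests would make the safety p-values fully valid. They would not. If the arm with the highest rate is picked after seeing the data and tested against the rest by chi-square, the true size is 0.075 at a 5% event rate and up to 0.142 at 20%. An exact test on the same selected arm does not remove that selection.

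**What to change.** In Section 12.1, and at both places in Section 12.2, replace chi-square by Fisher's exact test for two groups and Fisher-Freeman-Halton for four. State in 12.2 which comparison follows a noticed spike: four-arm, arm against placebo or arm against the rest.

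An exact Cochran-Armitage trend test over 0/20/40/80 IU may be added, but only as a supplement. When risk rises steadily with dose (5/10/20/50%) it has 64% power, against 47% for the four-arm chi-square and 39% for Fisher-Freeman-Halton. It has almost none for a spike in a lower dose. With 50% risk in the 40 IU arm and 10% elsewhere its power is 0.4%, against 40% for Fisher-Freeman-Halton, and for the same spike in the 20 IU arm it is 3%. As the main safety comparison it could hide such a signal.

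The cost is a few sentences in Section 12. The price is conservatism in two-group tables: Fisher's maximum size is 0.025 for 9 v 7 and 0.013 for 7 v 7, so some p-values will be larger. The bias from choosing the arm after seeing the data remains, and the report should say so.
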